6.3 Discontinuation

6.3.1 *Treatment Discontinuation*

If at any time during the study the investigator determines that it is not in the best interest of the subject to continue treatment, the subject's treatment will be discontinued. The investigator can discontinue the treatment for a subject at any time if medically necessary. If a subject's treatment is permanently discontinued by the investigator because of an AE, that AE should be indicated as the reason for treatment discontinuation. In this case, the subject is discontinued from the treatment, but still participates in the study and the subject is encouraged to follow the visit schedule and complete all assessments.

In addition, the investigator may instruct the subject to temporarily halt treatment of a specified region (i.e., due to an adverse event). This treatment modification and the reason for the temporary drug interruption should be documented in the subject's source documents and eCRF. The lesions in the impacted area should continue to be counted in the lesion count during the period of treatment modification.

The investigator may discontinue a subject's treatment if the subject/caregiver has failed to follow study procedures or to keep follow-up appointments. Appropriate documentation in the subject's study record and the study database regarding the reason for treatment discontinuation must be completed.

Reasons for an investigator's withdrawal of a subject **from the treatment** may include, but are not limited to, the following:

- Safety (e.g., severe adverse reactions, pregnancy)

- When a concomitant medication or treatment likely to interfere with the results of the study is reported, or required, by the subject, the investigator will decide, in consultation with the CRO whether the subject is to be withdrawn.

Reason(s) for discontinuation from the treatment as listed in the study record will be entered into the study database as follows:

- Completed (complete clearance prior to Week 12)
- Adverse Event (including LSRs deemed to be significant by investigator)
- Withdrawal by Subject/Caregiver
- Physician Decision
- Protocol Violation
- Lost to Follow-Up
- Pregnancy
- Lack of Efficacy
- Worsening of Molluscum Contagiosum
- Other

6.3.2 *Study Discontinuation*

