8.5 Dose and Administration

Subjects will apply treatment once daily for up to 12 weeks to all active lesions identified at baseline and new lesions that arise during treatment. If the investigator determines all lesions are cleared at a clinic visit, the treatment may stop. If treatment is stopped due to clearance, subjects will continue regularly scheduled visits through Week 24/ET2.

An increase in the number of MC lesions (with or without inflammatory reaction) during the early treatment phase is often observed. It is important to instruct the subject/caregiver to treat the new lesions as well as the existing lesions.

Each dose will consist of berdazimer gel or vehicle gel with hydrogel thoroughly mixed together by the subject or caregiver and applied to the lesions and approximately 1 cm surrounding each lesion. Periocular lesions will be treated if the lesions are at least 2 cm from the edge of the eye. If a subject has more than 20 MC, a second dose of berdazimer gel or vehicle gel with hydrogel can be prepared to ensure appropriate coverage of all lesions.

At the investigator's discretion, the subject may be placed on a drug holiday for up to 2 weeks at a time in the event of a significant local skin reaction (LSR). This will be captured in the electronic data capture (EDC) system and the subject's diary. The investigator should instruct the subject how long to hold study drug and the planned date to re-start treatment. Site staff should contact the subject on the day of the planned re-start and assess whether the LSR has resolved enough to resume treatment. If it has not resolved sufficiently, the drug holiday may be extended as long as the entire extension has not exceeded 2 weeks. If the LSR flares after re-introduction of study drug, the study drug should be permanently discontinued and the EDC system updated appropriately. Please see [Section 7.2.4](#) for additional information.

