4. STUDY DESIGN AND PLAN

This is a Phase 3 multi-center, randomized, double-blind, vehicle-controlled, parallel group study to be conducted in approximately 340 subjects ≥ 6 months of age with MC. After obtaining informed consent/assent, subjects who satisfy entry criteria will be randomized to a 2:1 (active:vehicle) scheme. Subjects receiving current treatment for MC at the time of the Screening Visit will enter a washout period of up to 14 days prior to randomization. In the event no washout period is required, Screening and Baseline visit activities may be combined into a single visit. At randomization, subjects will be stratified into 4 strata corresponding to the cross-classification of household number of randomly assigned subjects (1 subject per household vs 2 subjects per household) and investigator type (dermatologist vs other). Households randomizing 2 subjects will receive the same treatment assignment for both subjects. Up to 2 subjects from the same household may be randomly assigned on the same day, if both individually meet all inclusion and exclusion criteria. For subjects in the same household, Screening can occur on different days; however, the baseline visit must occur on the same day.

Subjects or their caregivers will apply SB206 12% or Vehicle Gel QD for a minimum of 4 weeks and up to 12 weeks to all lesions identified at Baseline and new treatable lesions that arise during the course of the study. Subjects or their caregivers will continue to treat the area until the next scheduled visit even if the lesion(s) clear. If the investigator determines all lesions are cleared at a clinic visit, the treatment may stop. At Weeks 2, 4, 8 and 12, the investigator will count and record the number of active (raised, treatable) molluscum lesions per body area. At Weeks 2, 4,

and 8, the investigator will determine if new lesions have occurred since the last visit, and the subject or caregiver will be instructed by the investigator to re-initiate treatment. If treatment is stopped due to clearance, subjects will continue regularly scheduled visits through Week 24.

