6. GENERAL ANALYSIS CONSIDERATIONS

The statistical analyses will be reported using summary tables, listings, and figures (TLFs). The International Council for Harmonisation (ICH) numbering convention will be used for all TLFs. Unless otherwise noted, all statistical testing will be 2-sided and will be performed at the 0.05 significance level. Tests will be declared statistically significant if the calculated *P*-value is ≤ 0.05 .

Continuous variable summaries will include the number of subjects (n) with non-missing values, mean, standard deviation (SD), median, minimum, and maximum. Other statistics such as quartiles, confidence intervals (CIs), and number of missing values may be added as appropriate.

Categorical variable summaries will include the frequency and percentage of subjects who are in the category or each possible value. In general, the denominator for the percentage calculation will be based upon the total number of subjects in the study population within each treatment group, unless otherwise specified. The denominator for by-visit displays will be the number of subjects in the relevant study population with non-missing data at each visit.

All summary tables will be presented by treatment group. Baseline summaries will also include an overall summary column.

Individual subject data obtained from the eCRFs and any derived data will generally be presented by subject in data listings. Additionally, a listing of the subjects requiring a narrative because they experience one of the following events: serious adverse event, death, discontinued the study due to an AE, hypertrophic or keloid scarring, unresolved scars, or LSR suggestive of allergic contact dermatitis will be presented.

The analyses described in this plan are considered a priori, in that they have been defined prior to breaking the blind.

Any analyses performed subsequent to breaking the blind will be considered post hoc and exploratory. Post hoc analyses will be labeled as such on the output and identified in the clinical study report.

All analyses and tabulations will be performed using SAS® software Version 9.4 or higher. Tables, listings, and figures will be presented in RTF format.

The process for SAS program validation and quality control (QC) for programs and outputs is documented in the Synteract working instruction “SAS programming quality control.” Study-specific QC requirements can be found in [Appendix C: SAS Programming QC Requirements](#).

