8. ANALYSIS POPULATIONS

The following subject population will be used for disposition analyses:

- The Enrolled Population will consist of all subjects who have a signed informed consent or assent. If a subject is randomly assigned to a treatment, then treatment assignment will be based on randomized treatment; otherwise, they will be deemed a screen failure and will only appear in the overall summary columns of output.

The following subject population will be used for safety analyses:

- The Safety Population will consist of all subjects who receive at least 1 application of study medication. Treatment assignment will be based on the treatment actually received. If a subject receives any amount of SB206, then they will be summarized in the SB206 12% QD arm.

The following subject populations will be used for efficacy analyses:

- The ITT Population will consist of all subjects who are randomized. Treatment assignment will be based on the randomized treatment.
- The Per-Protocol (PP) Population will consist of all subjects in the ITT Population who had no significant protocol deviations that impacted the analyses of efficacy endpoints. Final determination of subject inclusion in the PP Population will be made prior to unblinding. Treatment assignment will be based on the randomized treatment.

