13.2 Local Skin Reaction

The LSR composite score will be calculated by summing up all the numerical responses (0-4) to each individual parameter for a composite score that ranges between 0 and 24. The change from Baseline of the LSR composite score will be summarized descriptively. A table summarizing each LSR parameter (erythema, flaking/scaling, crusting, swelling, vesiculation/pustulation, and erosion/ulceration) score at each scheduled postbaseline assessment will be presented.

Additionally, a shift table comparing the baseline score for each LSR parameter to each scheduled postbaseline assessment will be presented for the Safety Population.

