14.3.1.3	Summary of Treatment-Emergent Adverse Events by System Organ Class, Preferred Term, and Maximum Severity	Safety
14.3.1.4	Summary of Treatment-Emergent Adverse Events by System Organ Class, Preferred Term, and Relationship to Study Drug	Safety
14.3.1.5	Summary of Serious Treatment-Emergent Adverse Events by System Organ Class and Preferred Term	Safety
14.3.1.6	Summary of Treatment-Emergent Adverse Events Leading to Study Drug Discontinuation by System Organ Class and Preferred Term	Safety

Table Number	Table Title	Analysis Population
14.3.1.7	Summary of Treatment-Emergent Adverse Events Leading to Death by System Organ Class and Preferred Term	Safety
14.3.2	Listings of deaths, other serious and significant adverse events	
14.3.2.1	Listing of Serious Adverse Events	Safety
14.3.2.2	Listing of Adverse Events Leading to Study Drug Discontinuation	Safety
14.3.2.3	Listing of Deaths	Safety
14.3.6	Other safety data	
14.3.6.1.1	Summary of Local Skin Reaction (LSR) Composite Score by Visit	Safety
14.3.6.1.2	Summary of Local Skin Reaction (LSR) Score Results by Visit	Safety
14.3.6.1.3	Shift Summary of Local Skin Reaction (LSR) Score Results by Visit	Safety
14.3.6.2	Summary of Events of Special Interest	Safety
14.3.6.3	Summary of Physical Examination Findings	Safety
14.3.6.4	Summary of Patch Testing Results	Safety

Figure Number	Figure Title	Analysis Population
14.2.1.5	Forest Plot: Odds Ratio (95% CI) of the Proportion of Subjects with Complete Clearance at Week 12	ITT
14.2.3.3.2	Percent Change from Baseline in Lesion Count over Time by Treatment Group	ITT
14.2.3.4.2	Mean Change from Baseline in Lesion Count over Time by Treatment Group	ITT
14.2.3.6.2	Kaplan-Meier Plot of Time to Complete Clearance (Days) from Start of Dosing	ITT
14.2.3.10.2	Plot of Complete Clearance at Week 12 by Highest Dichotomized Categorized BOTE Score	ITT

Section 16.2: List of Data Listings

ICH Listing Number	Listing Title	Analysis Population
16.1.7	Subject Randomization	ITT
16.2	SUBJECT DATA LISTINGS	
16.2.1	Discontinued subjects	
16.2.1.1	Subject disposition	Enrolled
16.2.2	Protocol deviations	
16.2.2.1	Protocol Deviations	ITT
16.2.2.2	Inclusion/Exclusion Criteria	Enrolled
16.2.3	Subjects excluded from the efficacy analysis	
16.2.3.1	Analysis Populations	Enrolled
16.2.4	Demographic data	
16.2.4.1	Demographic and Baseline Characteristics	ITT
16.2.4.2	Patch Testing Consent/Assent	Enrolled
16.2.4.3	Medical History	ITT
16.2.4.4	Prior and Concomitant Medications	ITT

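### Local skin reaction scores are tabulated only by visit, pooling subjects on and off drug, and no table shows each subject's worst score

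*Combined protocol and SAP*

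**What the plan says.** Final SAP 13.2 plans three LSR displays: change from Baseline in the 0 to 24 composite, the component scores, and a shift table. For the components it says "A table summarizing each LSR parameter (erythema, flaking/scaling, crusting, swelling, vesiculation/pustulation, and erosion/ulceration) score at each scheduled postbaseline assessment will be presented". Appendix D lists them as Tables 14.3.6.1.1 to 14.3.6.1.3, all by visit; the last is titled "Shift Summary of Local Skin Reaction (LSR) Score Results by Visit".

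Two general rules decide who is counted:

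- SAP 6: "The denominator for by-visit displays will be the number of subjects in the relevant study population with non-missing data at each visit".
- SAP 8: "The Safety Population will consist of all subjects who receive at least 1 application of study medication".

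Neither depends on whether the subject is still applying drug.

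Subjects who stop drug remain in the study. Protocol 8.5: "If the investigator determines all lesions are cleared at a clinic visit, the treatment may stop". SAP 4: "If treatment is stopped due to clearance, subjects will continue regularly scheduled visits through Week 24". When the investigator stops treatment for an adverse event, Protocol 6.3.1 says "the subject is encouraged to follow the visit schedule and complete all assessments". Protocol 7.2.4 and 8.5 also allow drug holidays for LSRs, and 7.2.4 keeps subjects with suspected allergic contact dermatitis on the schedule to Week 24 after a permanent stop.

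SAP 13.3 adds an any-time count per subject of LSR component scores of 1 or more, repeated with erythema counted only from 2. SAP 13.1 tabulates treatment-emergent adverse events by maximum severity.

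**The concern.** LSR is the trial's graded tolerability scale: six components, each scored 0 to 4. A reader of the LSR tables wants to know how bad the reactions get while the gel is in use. Tables by visit that ignore treatment status answer a different question: what the skin of all treated subjects with a score looks like on that date.

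The two questions diverge if subjects off drug are scored and their scores have fallen. Stops for clearance should be more common on SB206 if it works, so its column could be diluted more than the vehicle column. Reactions could then appear milder, and appear to fade over time, partly because fewer subjects are being exposed.

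Separately, by-visit tables cannot be added up into the share of subjects who ever reached a given grade. The SAP uses a worst-value summary elsewhere: maximum severity for adverse events (13.1) and the highest BOTE score on treatment (12). It has none for LSR.

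**Working it through.** The plan states no LSR figure to reproduce. The composite range is consistent: 6 components × 4 = 24.

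**1. Which visits can include off-drug subjects**

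- Clearance: SAP 4 sets a 4-week minimum of treatment. Under that rule a stop at the Week 4 visit first affects Week 8, and a stop at Week 8 affects Week 12. Subjects also keep treating up to the next visit if lesions clear between visits, and restart if new lesions appear.
- Holidays and reaction stops can affect any post-baseline visit.
- Protocol 8.5 allows a stop when the subject is found clear at a clinic visit and does not repeat the minimum. If that applied at Week 2, Week 4 would also be affected. The passages must be reconciled.

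**2. Are off-drug subjects scored?** SAP 4 and Protocol 4.1 have the LSR score recorded at every visit. Protocol Table 1 labels the row post-dose, and its footnote limits scoring to applicable visits, without defining these. If off-drug subjects are scored, dilution is possible. If they are not, they leave the denominator, and the later columns describe only subjects still on treatment.

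**3. Dilution if they are scored**

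Let p be the on-drug prevalence of a sign, q the share off drug, and r the off-drug prevalence relative to on-drug. The documents give none of these; all values here are assumed.

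Tabulated prevalence = p(1 − q) + r·p·q. With p = 50%:

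| q | r = 0 | r = 0.5 | r = 1 |
|---|---|---|---|
| 5% | 47.5% | 48.75% | 50% |
| 10% | 45% | 47.5% | 50% |
| 20% | 40% | 45% | 50% |

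Two arms, on-drug prevalence 50% vs 20% (difference 30 points), r = 0:

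- q = 10% vs 5%: 0.50 × 0.90 = 45%; 0.20 × 0.95 = 19%; difference 26 points.
- q = 20% vs 10%: 0.50 × 0.80 = 40%; 0.20 × 0.90 = 18%; difference 22 points.

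With r = 1 the difference stays at 30 points.

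**4. How many stops for reaction?** Protocol 1.2.2 reports no treatment discontinuation for an adverse event among the 48 Phase 2 subjects on 12% QD. The exact 95% upper limit is 1 − 0.025^(1/48) = 7.4%. Any dilution would therefore probably come mainly from clearance stops and holidays.

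**5. A pull in the other direction at Week 12.** Protocol 7.2.4 and 7.2.5 have the Week 12/ET1 assessments done when drug is stopped for suspected contact dermatitis, while the subject stays in the study. SAP 7 treats such a record as Week 12 if no Study Exit form has the same date. An acute score from an earlier week can therefore enter the Week 12 column and raise it.

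**6. By-visit versus ever.** Suppose a grade is seen in 10% of the 227 planned SB206 subjects at each of the four post-baseline visits (Weeks 2, 4, 8, 12). The share who ever had it is:

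- 10% if always the same subjects: 0.10 × 227 ≈ 23;
- 1 − 0.9⁴ = 34.4% if visits are independent: ≈ 78;
- 40% if never the same subject twice: 0.40 × 227 ≈ 91.

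The by-visit tables cannot tell these apart.

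**The case against.** A by-visit summary of all treated subjects is a legitimate safety display, and tolerability does not rest on it alone. The any-time counts in SAP 13.3 cannot be diluted by later zeros. Clinically significant LSRs are reported as adverse events and so enter the maximum-severity table and, where relevant, the table of events leading to drug discontinuation. SAP 9.4 counts subjects with interruptions, SAP 6 lists narratives for suspected contact dermatitis, and Listing 16.2.9.2 holds every LSR score. All of this stands: a reaction that resolved after stopping is not lost.

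These outputs still do not grade it. A threshold of 1 does not separate a slightly pink patch from black eschar, and raising the erythema threshold to 2 changes one component only. Adverse event severity covers only LSRs the investigator judged significant, and is graded by effect on daily activities (Protocol 9.2), not on the LSR scale.

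A reader might infer that SB206 reactions are in fact understated throughout Weeks 4 to 12. The documents do not support this: off-drug scoring is unclear, clearance stops fall mainly on Weeks 8 and 12, and Week 12 can be pushed either way. A reader might also take the planned Week 12 clearance rates (18% on vehicle, 18 + 18 = 36% on SB206) as the off-drug shares at Week 12. That counts subjects first found clear at Week 12, who by design were still applying drug up to that visit.

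**Conclusion.** The gap in reporting is real. All planned LSR tables are by visit, they ignore treatment status, and none shows the worst grade per subject. That the by-visit tables understate reactions during use is possible but not shown. It requires that off-drug subjects are scored and that their scores are lower. A larger effect on SB206 requires a larger off-drug share or higher on-drug reaction rates there. The size is unknown: under the assumptions above, the tabulated prevalence is 0.80 to 0.95 of the on-drug prevalence if off-drug subjects score zero, and equal to it if reactions persist.

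The point concerns the description of tolerability only; efficacy and type I error are untouched. It is a cheap improvement worth making, because a per-subject maximum is not diluted by later zeros and does not depend on which visit label an early-stop assessment receives. Its limit is that it sees only reactions present when LSR was scored.

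**What to change.** In SAP 13.2 and the table list:

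1. Add a table by arm of each subject's maximum post-dose score, for each component (0 to 4) and for the composite (0 to 24), from the Day 1 post-dose assessment through Week 12/ET1. Include scores taken at the visit when drug is stopped.
2. Keep the all-subject by-visit tables. As supportive only, show them by treatment status at the visit: on drug, on hold, stopped for clearance, stopped for reaction. Do not simply restrict them to subjects on drug. That would condition on tolerating the gel and remove those on hold or stopped for a reaction.
3. State whether subjects off drug are scored for LSR, reconciling the footnote on applicable visits with the text that has LSR recorded at every visit.
4. Reconcile the 4-week minimum with the passages that let treatment stop when the subject is found clear at a clinic visit.

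The LSR scores and treatment adjustments are already collected (Listings 16.2.9.2 and 16.2.5.3). The cost is one or two more tables and possibly a slightly less favourable tolerability figure.

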13.3 Events of Special Interest

Events of Special Interest will include subjects with any TEAE where the preferred term contains “application site”, subjects with at least 1 post-baseline occurrence of moderate BOTE inflammation score, or subjects with at least 1 post-baseline LSR component score ≥ 1 . A summary including the number and percentage of subjects with at least 1 event of special interest, AEs of interest by MedDRA system organ class and preferred term, at least 1 moderate BOTE inflammation score, and any LSR component score ≥ 1 will be provided for the Safety Population. The analysis will also be repeated with the LSR criteria revised to include any post-baseline LSR component (excluding erythema) score ≥ 1 and erythema score ≥ 2 .

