7.2.4 Local Skin Reaction Score

The investigator (or designated evaluator) will assess localized skin reactions (LSRs) at Baseline (at least 30 minutes post-dose), and at Weeks 2, 4, 8 and 12. The individual components of LSRs are scored separately on a scale of 0-4, with higher numbers indicating more severe reactions. The individual components include erythema, flaking/scaling, crusting, swelling, vesiculation/pustulation, and erosion/ulceration.

Compared to BOTE, LSR is generally more diffuse, associated with significant itch or tenderness, may necessitate discontinuation of study treatment and may need treatment for symptomatic relief (e.g. a topical corticosteroid or topical anesthetic). For very severe LSR, systemic corticosteroids may be considered.

Investigators will assess the treatment area at each scheduled visit and use their medical judgement to differentiate between BOTE and LSRs. When LSRs are clinically significant in the opinion of the investigator, s/he should report the condition as an AE(s) (e.g. application site erythema, application site edema).

In the event of an LSR, the investigator may choose to initiate a drug holiday for the study drug for up to 2 weeks; treatment with corticosteroids may be ordered during the drug holiday at the investigator's discretion. For very severe LSR, systemic corticosteroids may be considered. The subject should be instructed how many days to hold study drug and site staff should phone the

subject on the planned day of resuming study drug to ensure that the LSR has resolved. If the LSR has not resolved, the drug holiday may be extended as long as the total period of withholding study drug does not exceed 2 weeks. If the LSR has resolved, the subject may resume treatment. If the LSR flares again after re-introduction of study drug, allergic contact dermatitis may be suspected. The subject may again be treated with up to 2 weeks of corticosteroids.

If allergic contact dermatitis is suspected, study drug should be discontinued permanently and an AE of allergic contact dermatitis should be recorded as the reason for discontinuation. Week 12/ET1 assessments should be completed at the time of discontinuation, but the subject should continue in the study and complete study-related visits through Week 24.

Patch testing (see [Section 7.2.5](#) and [Section 20.2](#)) should be offered to the subject.

LSR Score

	Erythema	Flaking/ Scaling	Crusting	Swelling	Vesiculation/ Pustulation	Erosion/ Ulceration

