7.2.5 Patch Testing

In the event that a subject has an LSR that is felt to be suggestive of allergic contact dermatitis, patch testing may be initiated to confirm. This should be offered to the subject/caregiver. If the subject/caregiver consents to patch testing and once the LSR has been completely resolved for a period of 2 weeks and up to 2 months, patch testing will commence. Novan will provide the patch testing instruction once requested from the CRO medical monitor. Additional drug product for

patch testing may be supplied through IWRS if the currently assigned subject's investigational product has been assignment was > than 60 days of the patch testing date(s).

If allergic contact dermatitis is suspected, study drug should be discontinued permanently and an AE of allergic contact dermatitis should be recorded as the reason for discontinuation. Week 12/ET1 assessments should be completed at the time of discontinuation, but the subject should continue to participate in the study and complete study related visits through Week 24.

In the event of suspected allergic contact dermatitis, photographs may be taken of the affected area(s) and transmitted to the CRO medical monitor for review prior to initiating patch testing.

See [Section 20.2](#) for further information.

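### The adverse-event rule in SAP 13.3 matches only preferred terms containing 'application site', so an event recorded as allergic contact dermatitis can be missing from the adverse-event rows of Table 14.3.6.2

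*Combined protocol and SAP*

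**What the plan says.** Final SAP Section 13.3 (the SAP version that cites the Version 3.0 table shells) gives three routes into the Events of Special Interest summary:

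- Adverse events: "Events of Special Interest will include subjects with any TEAE where the preferred term contains" 'application site'.
- BOTE: "subjects with at least 1 post-baseline occurrence of moderate BOTE" inflammation score.
- Local skin reactions (LSRs): "subjects with at least 1 post-baseline LSR component score" of 1 or more.

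The summary (Table 14.3.6.2) shows subjects with any such event, a line each for the BOTE and LSR criteria, and "AEs of interest by MedDRA system organ class and preferred term". It is repeated with erythema counted only from score 2 and the other LSR components still counted from score 1.

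The protocol uses two vocabularies for local reactions. For ordinary clinically significant LSRs, the examples in Section 7.2.4 are "application site erythema, application site edema". For suspected sensitisation, the same section says that "an AE of allergic contact dermatitis should be recorded as the reason for discontinuation". Section 7.2.5 repeats this: "If allergic contact dermatitis is suspected, study drug should be discontinued permanently and an AE of allergic contact dermatitis should be recorded".

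**The concern.** The adverse-event criterion is a text match, and it fits the protocol's wording for ordinary local reactions but not its wording for suspected sensitisation. Neither document requires the latter to be coded to an 'application site' preferred term.

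The documents treat this event as important. Study drug stops permanently and patch testing is offered (protocol 7.2.4, 7.2.5). A separate procedure is set out for it (protocol 20.2), and final SAP Section 6 puts subjects with an LSR suggestive of it in the narrative listing. Local reactions are also the expected safety finding: protocol Section 1.1.4 says that administration site reactions were the only events clearly associated with SB206 in the Phase 2 molluscum study.

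What is at stake is whether the adverse-event rows of the special-interest table are complete. A reader could see application site erythema there by arm and not see allergic contact dermatitis.

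**Working it through.** The point rests on no sample size, power or error rate, so the plan has no figure to reproduce. The check sets the rule beside the terms the protocol supplies.

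**Step 1: the literal rule applied to the protocol's wording.**

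| Term in protocol 7.2.4 / 7.2.5 | Contains 'application site'? |
|---|---|
| application site erythema | yes |
| application site edema | yes |
| allergic contact dermatitis | no |

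**Step 2: from verbatim term to preferred term.** The SAP rule acts on the preferred term, whereas Step 1 tests reported wording. SAP Section 13.1 maps verbatim terms to MedDRA 22.0 preferred terms, and neither document gives the mapping for this event. There are two cases:

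- The coded term contains 'application site' (possible, for example, if a site writes those words before the diagnosis). The event is selected.
- The coded term keeps the protocol's wording or otherwise lacks those words. The event is not selected.

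Nothing in the documents excludes the second case, so omission is possible but not established.

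**Step 3: other ways for the subject to be counted in Table 14.3.6.2.**

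- *LSR criterion.* Allergic contact dermatitis is suspected when an LSR worsens or flares on re-starting study drug (protocol 4.1, 7.2.4). Week 12/ET1 assessments, which include LSR scoring, are due when drug is stopped for it. A component score of 1 or more is therefore likely.
- *An earlier application-site event.* Protocol 4.1 allows a drug holiday after a clinically significant LSR reported as an adverse event, or after subject-reported intolerance. In the first case the subject may already have an event whose term matches.

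Both routes count the subject. Neither adds a row for allergic contact dermatitis.

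**Step 4: other outputs that show the event.** If it is treatment-emergent, it appears by arm, system organ class and preferred term in Table 14.3.1.2. Because it must be recorded as the reason for stopping, it also belongs in the drug-discontinuation table (14.3.1.6) and listing (14.3.2.2). It is in the all-event listing (16.2.7.1), and the subject belongs in the narrative listing (16.2.9.6). Patch-test results, if any, are in listing 16.2.9.4. The patch-test summary is optional in final SAP 13.6, although Appendix D still lists it as Table 14.3.6.4.

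**Step 5: a separate limit.** SAP 13.1 ends the treatment-emergent window at the last application. A reaction with later onset would be outside Table 14.3.6.2 and the other adverse-event summaries whatever its term, and would appear only in listings. Changing the term rule does not alter that.

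**The case against.** The strongest reply is that the gap may never arise and would do little harm if it did. The preferred term is unknown, and most affected subjects would be counted by another route. The discontinuation table already gives a short display by arm in which allergic contact dermatitis would stand out. The protocol defines no special-interest category, so Section 13.3 is a descriptive supplement. All of this stands as a limit on size. It does not answer the point itself, because none of those outputs completes the adverse-event rows of Table 14.3.6.2.

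A reader might infer more than the documents support, in three ways:

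- *That the LSR criterion buries these subjects among those with slight pinkness.* The repeat analysis in Section 13.3 removes erythema score 1, and Section 13.2 shows each component by visit with shift tables. Mild scores on other components still count, so the LSR line does not identify sensitisation, but it does not conceal it either.
- *That a case triggers review by the DSMB.* Protocol 13.2 schedules that review for when about 200 subjects across the two studies have completed 4 weeks of treatment. It covers all available unblinded safety data, including patch testing, and a single case does not prompt it.
- *That a given number of cases would show as no event of interest.* The documents give no expected frequency, and subjects with an earlier application-site event would have a row for that event.

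**Conclusion.** The point holds as a minor completeness defect and a free improvement. As written, Section 13.3 can leave allergic contact dermatitis out of the adverse-event rows of the special-interest table. This rests on two conditions: sites follow the protocol's wording, and coding yields a preferred term without 'application site'. The documents neither confirm nor exclude the second.

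If both conditions hold, what is lost is a row in one targeted table. The subject usually remains in that table's counts, and a treatment-emergent event remains visible by arm in the overall and discontinuation tables. No efficacy result, hypothesis test or error rate is affected. A reading that a sensitisation signal would vanish from the report is not supported.

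**What to change.** Before unblinding, extend the adverse-event criterion in SAP 13.3 to treatment-emergent events whose preferred term contains 'application site' or is on a fixed list covering contact dermatitis and allergic contact dermatitis. Draw up the list from the MedDRA 22.0 terms while blinded, so that the choice of terms cannot depend on the results and the table does not depend on how a site or coder words the event. Give the event its own row in Table 14.3.6.2, displayed even when the count is zero.

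The cost is one sentence in the SAP, a short term list and one row in the table shell. It needs no new data and changes no clinical instruction. If the blind has already been broken, SAP Section 6 requires the added row to be labelled post hoc.
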